## Purpose

The purpose of the study is to improve upper limb function in people who have suffered injuries to their cervical spinal cord and have lost hand function. Many individuals with tetraplegia choose to undergo surgery, such as muscle-tendon transfers that restore function to their paralyzed upper limbs. In this study we will compare their ability to produce pinch force between the thumb and index finger before and after participating in a home exercise program. The exercises are designed to improve the strength and performance of the transferred muscle and also the muscles that are important to stabilize proximal joints.

The investigators anticipate the study will inform new postoperative treatment protocols designed to re-educate the transferred muscle in its new functional role. The objective is to determine if training to improve muscle strength and coordination will improve the ability to increase pinch strength after tendon transfer to restore pinch strength. Restoration of upper extremity function is rated among the highest priorities for individuals with tetraplegia. Use of the upper extremity is critical to functional independence, quality of life, ability to participate in society, and reduced burden of care.

## Study Procedures

**Recruitment and screening:** We will invite individuals to participate if they have a SCI resulting in tetraplegia with a previous tendon transfer surgery to restore their ability to pinch and grasp. Individuals with tetraplegia will be recruited from the Upper Extremity Clinics for Spinal Cord Injury at the VA Palo Alto Health Care System, Stanford University Hospital Clinics, and Valley Medical Center in San Jose, CA. A hand surgeon and the PI will attend all of the clinics. A letter may be sent to individuals who have expressed interest in previous studies to be contacted for participation in any new studies.

Participants will be scheduled for 1 to 2 test sessions in the Laboratory for Upper Extremity Research in the SCI Center (UE Lab). In the first session a set of measurements will be taken for baseline data of strength, muscle activation, and ability to perform functional pinch tasks. An fMRI study will be included in the first session. Each participant with tendon transfer procedures will be given a set of exercise equipment to take home. The equipment will include a set of weights for resistance exercise (i.e. lifting weights), a digital pinch meter for biofeedback of the pinch force, a table-top device that is used to provide target locations the participants reach for and to practice pinch (using variable resistance pinch pins) in locations that simulate the actual functional pinch tasks, and a task board with tasks that require pinch strength (ex: key, atm card, zipper).

The participants will get verbal and written instructions about how to use the equipment and a log-book to record their practice sessions. They will be instructed to practice the exercises for 10 weeks. A second appointment in the UE Lab will be scheduled to measure any changes in pinch function after the exercise program. A set of measurements that are identical to the baseline data set will be obtained, including the fMRI study.

**Home Exercise Training Program:** Participants will be instructed to use resistance exercises to strengthen elbow flexor and extensor muscle groups. The exercises should be done 3 times per week and should take about 30 minutes to complete. They will be instructed to do the strengthening exercises and practice pinching using the table-top device and the task board to practice producing pinch force in specific locations that simulate the position of an ATM machine, horizontal and vertical zippers, using a fork, electric plug, remote control, and a key. All of the instructions for performing the exercises will be provided and each participant will practice the home exercises at the first test session. The participants will receive a log- book to document their participation in the exercise program. The participants will not be able to keep the exercise weights, brace, pinch meter, or table-top device. They will be used for other participants who are enrolled in the study over the next 2 years. The equipment in the exercise kit will be cleaned with anti-bacterial soap after use by individual participants.

**Measurement of muscle structure and function:** Quantitative measurements of UE impairment will be recorded in the UE Lab. These measures include: muscle activation patterns with surface and fine- wire electrodes; and muscle strength using commercially available force transducers. A standardized test (Canadian Occupational

Performance Measure) designed to detect self-perceived changes in performance over time will be administered by the examiner. In the test, participants will be asked to identify daily activities they want to be able to do and those which are difficult to complete to your satisfaction. The questions will relate to self-care, productivity, and leisure activities. This survey will be completed by the examiner before and after the training program.

The participants will have an fMRI study to determine if the training program or the tendon transfer procedure produced changes in the brain compared to the control participants (non-impaired and SCI without tendon transfer surgery). During fMRI, the participants will lie on an MR table within the magnet and will be asked to lie as motionless as possible while they perform the task. The participant may also be fitted with a bite bar (made of dental impression material) to keep the head immobile during the scans. fMRI will be obtained during an active motor task during which participants are asked to perform lateral pinch tasks, or attempt upper limb movements. These tasks will be done at a submaximal level and participants will have feedback for the level of effort from the examiner.

We will minimize risk by using research procedures that are routinely used in the clinical management of persons with tetraplegia. The testing procedures are minimal risk and the participants may improve their pinch strength after the home program.

We will use video recording to document upper extremity motor performance during our clinical evaluation. The primary purpose of this information will be to document the testing procedures. However, these videos may be shown at scientific meetings. Participants will provide informed consent for all video recordings. Videos will be digitally stored on a password-protected computer. No personal health information will be linked to the video as they will be labeled using a unique patient identification codes. Videos will only include the participants arm and hand.

There is no standard treatment that is being withheld. All of the participants will have completed conventional clinical rehabilitation following their tendon transfer procedure. There are currently no post-rehabilitation options for patients to participate in after discharge. The home exercise program will not be continued following the 10-week participation time and the equipment must be returned.

**Study Endpoint:** Individuals who participate in the study will be monitoring their pinch strength during the 10-week exercise phase of the study and will be aware of any negative effects of exercise, such as losing strength. It is unlikely there will be a loss of function during a 10-week exercise program. This study will end once all the participants are enrolled or the funded project period ends.

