#### Statistical analyses

The main outcome measures for the fMRI data will be brain activation defined by intensity and cluster size in response to performing elbow flexion and pinch. Second level analyses will be mixed models effects derived using FSL FLAME for within participants (pre to post intervention) as well as cross-sectional (non impaired vs. SCI-n; SCI-n vs. SCI+TT) individual models (with outlier de-weighting and standard settings). Separately, T1 and T2 voxelwise models will regress EMG pinch amplitude for that time-point onto brain data to examine neural correlates of our standard EMG outcome metric. The difference between T1 and T2 will be tested similarly (fMRI con images and EMG calculated as [pre-post/pre+post]) before regressing EMG onto voxelwise brain data.

*Pinch and elbow extension strength.* Pinch force is sampled simultaneously with the EMG data. A custom MATLAB program is used to locate the peak force that is maintained for at least 0.5 sec during the 10 sec trial. Mean pinch force is expressed in newtons (1 lb. = 4.454 N) before and after the training period.

*EMG amplitude analysis.* The EMG signals recorded during maximal pinch and maximal elbow flexion will be quantified by calculating a root-mean-square value over a 0.5 sec interval during peak force production. The ratio of the EMG amplitudes during maximal pinch to those during maximal elbow flexion will be calculated to normalize the EMG signals. During maximum pinch effort, the normalized EMG signals will be used to compare the amplitude of the transferred Br activation before and after the training program in each of the trials

and between participants. The normalized EMG activation will be expressed as a percent of the maximum voluntary contractions (MVC).

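### The SCI control group is defined only by not having had a tendon transfer, so the one fMRI contrast that bears on the transfer is confounded by who receives one

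*Combined protocol and SAP*

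**What the plan says.** Study Procedures, Recruitment and screening, holds the only inclusion statement, which begins: "We will invite individuals to participate if they have a SCI resulting in tetraplegia with a previous tendon transfer surgery to restore their ability to". The same section gives the source: "Individuals with tetraplegia will be recruited from the Upper Extremity Clinics for Spinal Cord Injury". It names no source for people without SCI.

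The fMRI paragraph of Study Procedures asks whether the training or the transfer produced brain changes, "compared to the control participants (non-impaired and SCI without tendon transfer surgery". Statistical analyses turns this into "cross-sectional (non impaired vs. SCI-n; SCI-n vs. SCI+TT) individual models (with outlier de-weighting and standard settings". These come in addition to the within-participant pre-to-post models.

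Two phrases under Recruitment and screening show that some participants will have had no transfer: "Each participant with tendon transfer procedures will be given a set of exercise equipment to take home", and "Participants will be scheduled for 1 to 2 test sessions". A later sentence in Study Procedures reads the other way: "All of the participants will have completed conventional clinical rehabilitation following their tendon transfer procedure".

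**The concern.** The planned analysis needs three groups, and the protocol describes how to recruit one. For the non-impaired group this is mainly an omission. For SCI-n it goes to what the result would mean.

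The fMRI aim includes a causal question about the transfer procedure. Participants in SCI+TT have already had surgery when they enter, so their first scan is before training but after surgery. Their pre/post comparison can inform about training and cannot inform about surgery. Everything the study can say about surgery therefore comes from comparing SCI+TT with people who did not have it. If those people differ in injury level, residual arm function, time since injury or age, a difference in activation may reflect any of these and be reported as an effect of the transfer.

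**Working it through.** The plan states no sample size, group size, effect size or SD, so there is no figure to reproduce. The check is a comparison of sections.

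**1. Do the required groups meet the inclusion statement?**

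| Group | SCI with tetraplegia | Previous transfer | Described by the statement |
|---|---|---|---|
| SCI+TT | yes | yes | yes |
| SCI-n | tetraplegia not stated | no | no |
| Non-impaired | no | no | no |

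Neither of the two control groups is described. The general sentence on recruiting from the SCI clinics could supply SCI-n but not the non-impaired group.

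**2. Which planned comparison bears on the transfer?**

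- Within participants, pre to post: both scans of a transfer participant follow surgery, so this concerns training.
- Non-impaired vs SCI-n: neither group has had a transfer, so this concerns the injury.
- SCI-n vs SCI+TT: this is the only planned comparison in which transfer status differs.

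**3. What makes SCI-n and SCI+TT comparable apart from surgery?** The candidates in the text are:

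- Selection: SCI-n is defined by lack of a transfer. The clinics are at most a shared source.
- Matching: no factor is named.
- Adjustment: Statistical analyses names outlier de-weighting and standard settings for the group models. It names no covariate for the group contrasts.
- Design: there is no randomisation to surgery and no scan before it.

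None of these addresses injury level, residual arm function, time since injury or age.

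**4. Does the task add to the problem?** The fMRI paragraph lets participants either perform lateral pinch or attempt upper limb movements. SCI+TT participants had surgery to restore pinch. SCI-n participants may only be able to attempt it. A group difference on the pinch task could then be a difference between doing and trying. Statistical analyses also lists elbow flexion as an fMRI task, and this is less exposed because it does not depend on the restored pinch.

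**5. Illustration only, on assumed inputs.** Suppose activation correlates 0.3 to 0.6 with residual motor level, and the SCI groups differ by 0.5 to 1 SD in that level. With no transfer effect, the expected group difference is correlation × gap: 0.3 × 0.5 = 0.15 SD, up to 0.6 × 1 = 0.6 SD. For a two-sided 5% t-test with n per group, the non-centrality is d × √(n/2) on 2n − 2 degrees of freedom:

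| Assumed n per group | d = 0.15 | d = 0.6 |
|---|---|---|
| 10 | 0.062 | 0.246 |
| 20 | 0.075 | 0.456 |

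Every input is assumed, and a single t-test is not the planned voxelwise FLAME model, so these are not estimates for this study. They show only that the error can run from negligible to large, and that enrolling more people does not reduce it.

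**The case against.** A reader might infer that the protocol bars the control groups from enrolment. The text does not support that. The inclusion sentence says who will be invited and does not say that nobody else will be. The home kit is reserved for participants with transfers, and one session is allowed for. The fMRI paragraph and Statistical analyses both name the controls. The sentence about rehabilitation after the transfer sits in a paragraph on withheld treatment and the exercise programme, where the participants meant are most naturally those in the programme. It is loose wording rather than a second enrolment rule.

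A reader might also infer that SCI-n is open to anyone with tetraplegia, including people with natural pinch or with no arm movement. That goes too far. Purpose describes people who have lost hand function, and the clinics are upper-extremity SCI clinics attended by a hand surgeon. Elbow flexion is one of the fMRI tasks, which limits the second example, although attempted movement is allowed. The documents also do not say how patients are selected for transfer, so the direction of any imbalance cannot be stated.

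Finally, the main objective in Purpose is the within-person change in pinch, which does not use the controls. That is correct and limits the scope of the point.

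What remains is comparability. A shared clinic and a general description of the population do not make the two SCI groups alike in level, residual function, time since injury or age, and no adjustment is planned.

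**Conclusion.** The point holds for one contrast and one stated aim. The missing control eligibility is an omission that can be filled from the evident intent. The lack of any selection, matching or adjustment for SCI-n is more serious. As written, SCI-n vs SCI+TT cannot separate the effect of the transfer from differences between people who have had one and people who have not, and no other planned analysis can do so.

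The size of the bias cannot be derived from the documents. The conclusion does not depend on the assumed figures in the working. It rests on three features of the text: surgery precedes all scans, group membership is not randomised, and SCI-n is defined only by the absence of surgery. This point does not affect the within-person pre/post comparisons of pinch, EMG and fMRI. The change should be made before control participants are scanned, because an unsuitable control group is hard to repair afterwards.

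**What to change.** 1. In Recruitment and screening, admit both control groups explicitly, with criteria, source and target number for each.
2. Define SCI-n as people with tetraplegia from the same clinics who are judged eligible for the same pinch transfer but have not had it.
3. Keep SCI-n similar to SCI+TT in motor level and time since injury where feasible. Strict matching on several factors may not be achievable, so otherwise enter motor level, and age if numbers allow, as covariates in the group models in Statistical analyses.
4. State that inference for SCI-n vs SCI+TT rests mainly on the elbow-flexion task, and record whether pinch was performed or only attempted. Restricting SCI-n as in item 2 does not remove that difference.
5. Report the contrast as an association, not as an effect of the transfer.
6. Limit the sentence about rehabilitation after transfer to the tendon-transfer group.

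The cost is an eligibility amendment and a short addition to the analysis text. No new procedure is needed. The downside is a narrower SCI-n pool and slower accrual. The documents do not say how many eligible people without a transfer attend these clinics, so feasibility should be checked first. If too few are available, covariate adjustment and the associational label are the minimum.

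### The fMRI aim claims brain changes produced by training or tendon transfer relative to controls, but no planned analysis compares change with controls, and the SCI+TT scan used in the transfer contrast is not named

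*Combined protocol and SAP*

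**What the plan says.** **Aim.** Study Procedures (fMRI paragraph) says the scans are to "determine if the training program or the tendon transfer procedure produced changes in the brain compared to the control participants". It names two control groups: non-impaired people, and people with SCI who have not had a tendon transfer.

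**Who is trained, and when surgery happened.** Recruitment is of people with "a SCI resulting in tetraplegia with a previous tendon transfer surgery to restore their ability to pinch and grasp". Training goes to that group: "Each participant with tendon transfer procedures will be given a set of exercise equipment to take home". Surgery and the care after it are complete before entry: "All of the participants will have completed conventional clinical rehabilitation following their tendon transfer procedure".

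**Scans.** The first session includes an fMRI study. After the 10-week programme, "A set of measurements that are identical to the baseline data set will be obtained, including the fMRI study". The number of sessions is given as one or two, without saying which group has which number.

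**Analyses.** The fMRI paragraph of Statistical analyses lists second-level models "for within participants (pre to post intervention"), and "cross-sectional (non impaired vs. SCI-n; SCI-n vs. SCI+TT) individual models". Separately, "T1 and T2 voxelwise models will regress EMG pinch amplitude for that time-point onto brain data", and the T1-T2 difference in brain data is related to the EMG difference in the same way.

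**The concern.** The aim is causal (it asks what training or surgery produced), it is about change, and it is judged against controls. To support it, the plan would need a comparison of change between trained people and controls, and, for surgery, some observation of the brain before the operation. The analysis section contains neither.

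Two misreadings become likely if results are reported against that aim. Drift or familiarity with the scanner task between sessions could be taken for a training effect. Differences between people who do and do not have surgery could be taken for an effect of surgery; the Purpose section itself describes surgery as something that many people with tetraplegia opt for. In addition, leaving the SCI+TT scan open lets the training change enter the transfer contrast, and lets the choice be made after results are seen.

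**Working it through.** The plan gives no figure to reproduce on this point, so the check sets the aim against each listed analysis.

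**Readings used.** SCI-n is not defined. It is read as SCI without tendon transfer, since non-impaired people are listed separately and those are the only two control groups named. T1 and T2 are read as before and after training.

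**Step 1: list the group-level fMRI analyses.** The count is 1 pre-post + 2 cross-sectional + 2 single-time EMG regressions + 1 EMG regression on the difference = 6.

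| Analysis | Uses change? | Control comparison named? |
|---|---|---|
| Pre-post within participants | Yes | No |
| Non-impaired vs SCI-n | No | Between the two control groups only |
| SCI-n vs SCI+TT | No | Yes, but cross-sectional only |
| EMG regression at T1 | No | No |
| EMG regression at T2 | No | No |
| EMG regression on T1-T2 difference | Yes | No |

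- Analyses that use change: 2 of 6.
- Analyses that compare change with controls: 0 of 6.
- Analyses that compare transfer with no transfer: 1 of 6, and only cross-sectionally.

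**Step 2: training.** Only people with a transfer receive the programme, so

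mean pre-post change = training effect + time/retest effect.

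No control change is subtracted. The T1-T2 EMG regression asks whether people whose EMG changed more also show more brain change. It does not remove time or retest effects from the mean change.

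**Step 3: transfer.** With surgery before entry and no pre-surgery scan described,

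SCI+TT minus SCI-n, using T1 = transfer effect + selection differences.

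The two terms cannot be separated with the data described.

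**Step 4: choice of scan.** Using T2 instead,

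SCI+TT minus SCI-n, using T2 = transfer effect + selection differences + training effect + time/retest effect.

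Write A1 and A2 for the SCI+TT means at T1 and T2, and C for the SCI-n mean. Then

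(A2 − C) − (A1 − C) = A2 − A1.

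The choice of scan therefore moves the contrast by the whole mean pre-post change. This is exact for unweighted means over the same participants, and approximate under FLAME with outlier de-weighting. The plan ties the EMG regressions to a time point but gives none for SCI-n vs SCI+TT: two scans are scheduled per SCI+TT participant and none is designated.

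**The case against.** The strongest reply is that the aim sentence is a plain-language description of why scans are done, while the analysis section makes no claim of controlled change and labels its models accurately as within-participant and cross-sectional. On a looser reading, SCI-n vs SCI+TT is the comparison with controls. This makes the harm conditional on how results are reported. It does not remove the mismatch: the aim speaks of changes that were produced, and a difference at one time is not a change.

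A second reply is that the pre-training scan is the natural default, because the first session is the baseline and the second follows the exercise programme. That is the sensible reading, but it is not written down. Use of T2 scans is a possibility left open, not something the plan states.

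A third is that the missing control for training and the missing pre-surgery scan are limits of the design, and that rewording changes no estimate. This is correct, and it is why the remedy for those two parts is wording. Only the scan designation changes an analysis.

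It is also fair that the counts measure text rather than bias, and that the total of six would grow if the two tasks or the two activation measures were counted separately. The zero for controlled change does not depend on how the models are counted.

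Finally, repeat control scans with a group-by-time contrast could address the training half of the aim. The plan states no repeat scan for controls, and even if some are rescanned, no analysis listed would use them to compare change.

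**Conclusion.** The concern holds. As written, the fMRI aim claims something that the design and listed analyses cannot show: 0 of 6 analyses compare change with controls, and the single transfer contrast is an association. The SCI+TT scan for that contrast is unspecified, and the choice matters by the full mean pre-post change in that group.

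The bias cannot be sized in activation units, because the documents give no sample size, activation values or retest data. The conclusion rests on the readings of SCI-n and of T1/T2 given above. Two scans per SCI+TT participant is the schedule; people who do not return will have one. The point should be corrected, but it is limited to the fMRI conclusions and leaves the pinch-strength objective untouched.

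**What to change.** 1. In Statistical analyses, state that SCI-n vs SCI+TT uses only the T1 (pre-training) scans of SCI+TT participants. T2 scans then enter only the pre-post model and the EMG regressions.
2. In the fMRI paragraph of Study Procedures, and in the conclusions drawn from it, restate the aim as (a) within-participant change after training, uncontrolled for time and retest, and (b) a cross-sectional difference associated with tendon transfer. Make no claim that either produced change relative to controls.

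The cost is one sentence in Study Procedures and one detail in Statistical analyses, with no new scans, visits or participants. The price is a more modest, non-causal conclusion.

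### Does a study-end rule that never mentions the post-training session leave late trainees without a second measurement?

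*Combined protocol and SAP*

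**What the plan says.** The only rule for ending the study stands under Study Endpoint in Study Procedures: "This study will end once all the participants are enrolled or the funded project period ends". Two other parts of the document bear on it.

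- **Timing and content of the second session (Study Procedures).** Of the trainees, the recruitment and screening text says "They will be instructed to practice the exercises for 10 weeks". It continues: "A second appointment in the UE Lab will be scheduled to measure any changes in pinch function after the exercise program", and "A set of measurements that are identical to the baseline data set will be obtained, including the fMRI study". On the Canadian Occupational Performance Measure (COPM), the measurement section says "This survey will be completed by the examiner before and after the training program". A later paragraph limits each person's training: "The home exercise program will not be continued following the 10-week participation time and the equipment must be returned". That limit concerns the individual's program and not the study.
- **Use of the two sessions (Statistical analyses).** The fMRI models are "within participants (pre to post intervention) as well as cross-sectional (non impaired vs. SCI-n; SCI-n vs. SCI+TT) individual models". There are voxelwise EMG regressions at T1 and at T2, and then "The difference between T1 and T2 will be tested similarly". Pinch force and normalized EMG are also compared before and after training.

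**The concern.** The second session can take place no sooner than 10 weeks after the first. A study that stops on the day the last person enrols, or on the day funding ends, could therefore close while some trainees are still exercising. Nothing in the text stops trainee enrolment ahead of the funding date, and nothing says how a trainee without a second session is analysed.

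Such a trainee would still serve the T1 regression and could serve the cross-sectional models. The same person would be lost to the T2 regression, the T1-T2 difference model, the within-participant fMRI model, and the pre-post comparisons of pinch force, EMG and COPM. The Purpose section makes the change in pinch force the central question, so the loss would fall on the comparison that matters most. The remedy that suggests itself is to tie study end to the last trainee's second session and to close trainee enrolment at least 10 weeks before funding ends.

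**Working it through.** The plan has no figure of its own to reproduce: it states no sample size, accrual rate, funding date or enrolment window. The only input from the documents is the 10-week training period. The 2 years mentioned under Home Exercise Training Program concern reuse of equipment and are not a stated enrolment window. Windows of W = 52, 104 and 156 weeks are assumptions, as are uniform enrolment at r trainees per week up to closure and no visits afterwards.

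**Step 1. Share without a second session.** Share = 10 / W.

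- 10/52 = 19.2%; 10/104 = 9.6%; 10/156 = 6.4%.
- With a further assumed 4 weeks to schedule the visit: 14/52 = 26.9%; 14/104 = 13.5%; 14/156 = 9.0%.
- If trainee enrolment happens to finish at least 10 weeks plus scheduling time before closure: 0%.

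**Step 2. Apparent cost in precision.** Against a study in which every trainee is retested, the standard error of a mean paired change grows by 1/√(1 − share): 1.113, 1.052 and 1.034 for the three windows with a 10-week tail. This is the right comparison only if the sample size is fixed and the study really stops at the last enrolment.

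**Step 3. Is that reading tenable?** Set beside the end rule, the recruitment and screening text promises a second appointment and a full repeat of the baseline measurements, with no exception for late entrants. The COPM is required after training. The paragraph that contains the end rule itself treats the 10 weeks of exercise as a phase of the study. Stopping at the last enrolment would contradict all three. The reading that fits them is that recruitment stops once enrolment is complete.

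**Step 4. The funding condition.** Here the end date is fixed at W. Compare the present text with closing trainee enrolment at W − 10:

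| | Present text | Early closure |
|---|---|---|
| Trainees with a first session | rW | r(W − 10) |
| Complete T1-T2 pairs | r(W − 10) | r(W − 10) |
| First session only | 10r | 0 |

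For W = 104, that is 94r pairs either way (104 − 10 = 94). The ratio of standard errors is √(94r/94r) = 1.00, and the same cancellation holds for any W. Late trainees are not rescued by early closure; they are simply never enrolled. What early closure does change is the first-session data: 10r of rW trainee observations disappear, which is again 19.2%, 9.6% or 6.4% for the three windows (26.9%, 13.5% or 9.0% with the scheduling allowance). The T1 and cross-sectional models could have used those observations.

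**The case for a change.** The strongest case for a change is that the two conditions are joined by an *or*. A generous reading of the enrolment condition therefore does not cure the funding condition. Enrolment is evidently staggered, since exercise kits pass from one participant to the next, so a late tail is plausible. Two or three sentences would settle the matter, and the document is silent on how to handle and report trainees without a second session.

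Much of this stands as description. The sentence is ambiguous, no other end rule exists, and no enrolment cut-off is written down. It does not show that a change would improve the analysis. Under the funding condition the proposed cut-off adds no pairs and costs first-session observations. The remaining argument for it is to spare people a program they could not complete and be retested on, which is a matter of ordinary site scheduling. Nothing in the documents suggests that trainees would be enrolled into the final weeks or that second visits would be cancelled. As for reporting, a paired comparison uses the people with both measurements, and a competent analyst would state how many lacked the second one and why without being told to.

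**Conclusion.** The concern does not call for a change. The enrolment condition is loose wording for the end of recruitment, as the unconditional commitment to a second session shows. The funding condition is an administrative limit, and writing in an earlier cut-off for trainees would leave the number of complete pairs unchanged (standard-error ratio 1.00) while giving up first-session data. The increases of about 11%, 5% and 3% in standard error apply only to the literal enrolment reading with a fixed sample size, which the surrounding text contradicts.

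The share of trainees affected is not derivable from the documents and may be 0%. Every non-zero figure above depends on an assumed window, uniform enrolment right up to closure, and no visits after closure. Loss caused by a calendar date is administrative, and the documents give no reason to link it to outcome, so precision is the only thing in question. Saying plainly that completed enrolment ends recruitment only would help a reader, but it is optional.
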